8.1. Discontinuation from Study Treatment

8.1.1. *Permanent Discontinuation from Study Treatment*

Patients for whom investigational product should be permanently discontinued, irrespective of the reason, should complete the Post-Treatment Follow-Up and then be permanently discontinued from the study. Section 8.2 provides the list of criteria for permanent discontinuation of patients from study treatment and the study.

Patients discontinuing from the investigational product prematurely for any reason should complete AE and other follow-up procedures per Section 2 (Schedule of Activities), Section 5.1.4 (Post-Treatment Follow-up Period), Section 9.2 (Adverse Events), and Section 9.4 (Safety) of this protocol.

8.1.2. *Temporary Interruption (Withholding) of Study Treatment*

Some possible reasons for temporarily withholding investigational product include, but are not limited to:

- Development of:
 - Serious or opportunistic infections, as described in Section 9.2.3).
 - Hypertension (see Section 9.4.2.1).
 - Latent TB infection (LTBI) (see Section 9.4.5.2).
 - Positive HBV DNA results that are below the level of quantification (see Section 9.4.5.4).
 - Hepatic event or liver test abnormality: Investigational product should be withheld and additional testing performed following consultation with the Lilly-designated medical monitor, if the results of repeat tests following elevated ALT, ALP or total bilirubin level (TBL) include one of the following (Section 9.4.6.1):
 - ALT ≥ 3 x ULN and TBL < 2 x ULN
 - ALP ≥ 2 x ULN and TBL < 2 x ULN
 - TBL ≥ 2 x ULN without increase from baseline in ALT/AST/ALP.
- Surgery: Patients requiring surgery at any time during the study should interrupt administration of the investigational product, beginning 8 weeks before the surgery or as early as possible within 8 weeks of surgery, and resume administration of the investigational product only after complete wound healing.

Cases that may merit temporary withholding of the study treatment should be discussed with the medical monitor. The medical monitor, in consultation with the investigator, will determine when it is appropriate to recommence study treatment.

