8.2. Discontinuation from the Study

Patients should permanently discontinue the investigational product, complete the Post-Treatment Follow-up, and then permanently discontinue from the study for any of the following reasons:

- **Subject Decision**
 - The patient requests to be either discontinued from the investigational product or withdrawn from the study.
- **Discontinuation due to a hepatic event or liver test abnormality.** Patients who are discontinued from investigational product due to a hepatic event or liver test abnormality should have additional hepatic safety data collected via eCRF.

Discontinuation of the investigational product for abnormal liver tests should be considered by the investigator when a patient meets one of the following conditions after consultation with the Lilly-designated medical monitor:

- ALT or AST >8x ULN
- ALT or AST >5x ULN for more than 2 weeks
- ALT or AST >3x ULN and TBL >2x ULN or international normalized ratio (INR) >1.5
- ALT or AST >3x ULN, with the appearance of fatigue, nausea, vomiting, right upper-quadrant pain or tenderness, fever, rash, and/or eosinophilia (>5%)
- ALP >3x ULN
- ALP >2.5x ULN and TBL >2x ULN

- ALP >2.5x ULN, with the appearance of fatigue, nausea, vomiting, right quadrant pain or tenderness, fever, rash, and/or eosinophilia (>5%)
- In addition, patients who meet any one of the following criteria should be discontinued from the investigational product, enter the Post-Treatment Follow-Up Period, and discontinue from the study:
 - Total white blood cell (WBC) count <2000 cells/ μ L (<2.00 x 10³/ μ L or <2.00 GI/L).
 - Lymphocyte count <500 cells/ μ L (<0.50 x 10³/ μ L or <0.50 GI/L).
 - Platelet count <50,000 cells/ μ L (<50 x 10³/ μ L or <50 GI/L).
 - Changes in blood pressure (BP) (systolic BP at \geq 160 mm Hg plus \geq 20 mm Hg increase from baseline [Week 0; Visit 2]; and/or diastolic BP at \geq 100 mm Hg plus \geq 10 mm Hg increase from baseline) that do not respond following maximal allowed intervention (further explanation in Section 9.4.2.1).
 - The patient experiences a severe AE, an SAE, or a clinically significant change in a laboratory value that, in the opinion of the investigator, merits the discontinuation of the investigational product.
 - Clinically significant systemic hypersensitivity event following administration of investigational product.
 - The patient becomes pregnant.

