 - The patient develops a malignancy (Note: patients may be allowed to continue if they develop no more than 2 non-melanoma skin cancers during the study).
 - Any patient who has a change in disease phenotype at any time (for example, a change to pustular psoriasis).
 - If the patient remains at or above their baseline sPGA score at Week 16 (Visit 7) and Week 24 (Visit 9), or remains at or above their baseline PASI score at Week 16 (Visit 7) and Week 24 (Visit 9).
 - It is recommended that the patient be assessed by an appropriately trained professional to assist in deciding whether the patient is to be discontinued from study treatment and the study if:
 - i. The patient, at any time during the study, scores a 3 for Item 12 (Thoughts of Death or Suicide) on the 16-item Quick Inventory of Depressive Symptomatology (QIDS-SR16);

OR

- ii. Develops active suicidal ideation with some intent to act with or without a specific plan (“yes” to question 4 or 5 on the “Suicidal Ideation” portion of the C-SSRS);
OR
- iii. Develops suicide-related behaviors as recorded on the C-SSRS.
 - The patient develops active TB or HIV/AIDS during the study.
 - The patient becomes HBV DNA or HCV RNA positive. The patient should be referred to a specialist physician (see Sections 8.1.2 and 9.4.5.4 for HBV, and Section 9.4.5.5 for HCV).
- Patients will also be permanently discontinued from study drug, complete Post-Treatment Follow-up, and then permanently discontinued from the study in the following circumstances:
 - Enrollment in any other clinical study involving an investigational product or enrollment in any other type of medical research judged not to be scientifically or medically compatible with this study
 - Participation in the study needs to be stopped for medical, safety, regulatory, or other reasons consistent with applicable laws, regulations, and GCP
 - Investigator decision
 - The investigator decides that the patient should be discontinued from the study
 - If the patient, for any reason, requires treatment with another therapeutic agent that has been demonstrated to be effective for treatment of the study indication, discontinuation from the study occurs prior to introduction of the new agent

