Patients permanently discontinuing from investigational product, completing the Post-Treatment Follow-Up, and permanently discontinuing from the study prematurely for any reason should complete AE and other safety follow-up per Section 2 (Schedule of Activities), Section 5.1.4 (Post-Treatment Follow-up Period), Section 9.2 (Adverse Events), and Section 9.4 (Safety) of this protocol.

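### Protocol 8.2's new-agent bullet, read with its lead-in, can be taken to bar another effective psoriasis agent until follow-up is complete, whereas 5.1.4 and 7.7 allow one once follow-up is entered

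*Protocol*

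**What the plan says.** The last group of discontinuation circumstances in Protocol 8.2 opens by stating that patients will be taken off study drug, "complete Post-Treatment Follow-up, and then permanently discontinued from the study in the following circumstances". One of the circumstances beneath it, under investigator decision, is that the patient "requires treatment with another therapeutic agent that has been demonstrated to be effective for treatment of the study indication". For that patient, "discontinuation from the study occurs prior to introduction of the new agent".

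Protocol 5.1.4 (Post-Treatment Follow-up Period) and the end of Protocol 7.7 (Concomitant Therapy) carry an identical permission: a patient who has entered follow-up may receive another psoriasis agent that the investigator judges appropriate. Footnote s of the Schedule of Activities places entry into follow-up directly after the early termination visit. Footnote t requires every treated patient who does not join Study AMAH to enter follow-up and complete V801 and V802.

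**The concern.** Both sets of text answer the same question: when may a patient who has stopped study drug start another effective psoriasis treatment? Under 5.1.4 and 7.7 the answer is from the start of follow-up. Under the 8.2 bullet, with leaving the study defined as its lead-in defines it, the answer is after follow-up has ended.

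Timely access to treatment is what is at stake. The bullet applies to the very patients who need other therapy, and a site that follows it to the letter could make them wait. Sites that work from 5.1.4 would not, so practice could differ between sites. The estimate of treatment effect is not at stake.

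**Working it through.** There is no plan figure to reproduce. The check sets the passages side by side and then measures the gap between the two rules.

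**Step 1: the order in 8.2.** Lead-in: stop study drug, complete follow-up, then discontinue from the study. Bullet: discontinue from the study, then start the new agent. Chained, these give: stop study drug, complete follow-up, leave the study, new agent.

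**Step 2: the order in 5.1.4 and 7.7, with footnote s.** Stop study drug, early termination visit, enter follow-up; a new agent is allowed from that point.

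**Step 3: is the lead-in an isolated slip?** Sections 8.1.1 and 8.2 state the sequence five times:

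- 8.1.1: "should complete the Post-Treatment Follow-Up and then be permanently discontinued from the study". Explicit order.
- 8.2, opening sentence: "complete the Post-Treatment Follow-up, and then permanently discontinue from the study for any of the following reasons". Explicit order.
- 8.2, the lead-in to the new-agent bullet, quoted above. Explicit order.
- 8.2, closing paragraph: "completing the Post-Treatment Follow-Up, and permanently discontinuing from the study prematurely for any reason". Same order, but as a plain list without *then*.
- 8.2, the lead-in that begins *In addition*: "enter the Post-Treatment Follow-Up Period, and discontinue from the study". Follow-up need only be entered.

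So three of five state explicitly that follow-up is completed first, one lists that order without insisting on it, and one differs. The one that differs governs the Week 16 and Week 24 no-benefit criterion, so that criterion is outside this point.

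**Step 4: the gap.** Input: V802 is scheduled at last visit plus 12 weeks, Day 85 ± 5 (Schedule of Activities), taking the last visit as Day 1.

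- Nominal: 85 − 1 = 84 days (12 × 7 = 84).
- Earliest: 80 − 1 = 79 days.
- Latest: 90 − 1 = 89 days.

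These are maxima. They apply to a patient who needs the new agent on the day follow-up is entered. If the need arises k days later, the nominal gap is 84 − k.

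**Step 5: how many patients.** The documents do not give the share of early leavers who would need another effective agent, so no count can be derived.

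**The case against.** The strongest reply is that the protocol already answers the question where a site would look. Section 7.7 governs concomitant therapy, 5.1.4 governs follow-up, and both give the permission outright. The closing paragraph of 8.2 itself refers patients who leave early to 5.1.4. Moreover, 5.1.2 and 5.1.3 use discontinuing the study for the event that comes before the early termination visit and follow-up. In that sense the bullet only requires the patient to leave blinded treatment first, and it agrees with 5.1.4. The rationale in Appendix 7 for adding the permission to 5.1.4, faster access for patients without benefit, points the same way.

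Most of this stands, and it settles the likely intent. It does not remove the literal reading. The bullet sits under a sentence that places study discontinuation after completed follow-up, so a site must bring in a looser meaning from another section to reach the intended rule. The closing paragraph refers to 5.1.4 for safety follow-up procedures and does not say that it overrides the bullet. Appendix 7 lists a change to 8.2 only for hypersensitivity, which suggests that the bullet was left behind. Appendix 7 is used here only as evidence of intent; the conflict is between sections of the current text.

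A reader might go further and infer three things that the documents do not support:

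- *That 8.2 flatly prohibits a new agent during follow-up.* No single sentence says so. It is one available reading, set against two express permissions.
- *That about 100 patients are exposed.* The synopsis plans 500 randomized and 400 completed, and 500 − 400 = 100, but that is every planned non-completer. It includes exits under the no-benefit criterion and exits where no other agent is needed.
- *That every affected patient waits 84 days.* That is the upper end, as Step 4 shows.

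**Conclusion.** The inconsistency is real and minor. The 8.2 bullet, read with its lead-in, can be taken to withhold another effective psoriasis agent until follow-up is complete, and that contradicts 5.1.4 and 7.7. The latter pair is very probably what was meant.

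The possible delay is up to about 84 days (79 to 89). This assumes that a site applies 8.2 literally and that the patient needs the agent on entry to follow-up. The number of patients affected cannot be estimated, and variation between sites is a possibility, not something the documents show. No efficacy or safety analysis is affected, and V801 and V802 are required under either rule. Confidence is high that the wording conflicts, and much lower that any patient would actually be delayed.

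**What to change.** Reword the 8.2 bullet along these lines: *study treatment is stopped and the Post-Treatment Follow-Up Period is entered before the new agent is introduced (see Sections 5.1.4 and 7.7)*.

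This brings the three sections into line and keeps the safeguard that study drug stops before another effective agent starts. The cost is one reworded bullet, with no new data, visits or analyses.

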8.3. Lost to Follow-Up

A patient will be considered lost to follow-up if he or she repeatedly fails to return for scheduled visits and is unable to be contacted by the study site. Site personnel are expected to make diligent attempts to contact patients who fail to return for a scheduled visit or were otherwise unable to be followed up by the site.

9. Study Assessments and Procedures

Section 2 lists the Schedule of Activities, with the study procedures and their timing (including tolerance limits for timing).

Appendix 2 lists the laboratory tests that will be performed for this study.

Unless otherwise stated in the subsections below, all samples collected for specified laboratory tests will be destroyed within 60 days of receipt of confirmed test results. Certain samples may be retained for a longer period, if necessary, to comply with applicable laws, regulations, or laboratory certification standards.

9.1. Efficacy Assessments

9.1.1. Primary Efficacy Assessments

The primary efficacy endpoints are the proportion of patients with an sPGA (0,1) with at least a 2-point improvement from baseline at Week 16 and the proportion of patients achieving a $\geq 90\%$ improvement in PASI from baseline (PASI 90) at Week 16.

9.1.1.1. Static Physician's Global Assessment

The sPGA is the physician's global assessment of the patient's psoriasis lesions at a given time point (EMA 2004). Plaques are assessed for induration, erythema, and scaling, and an overall rating of psoriasis severity is given using the anchors of clear (0), minimal (1), mild (2), moderate (3), severe (4), or very severe (5).

9.1.1.2. Psoriasis Area and Severity Index

The PASI is an accepted primary efficacy measurement for this phase of development of psoriasis treatments (EMA 2004). The PASI combines assessments of the extent of body-surface involvement in 4 anatomical regions (head, trunk, arms, and legs) and the severity of scaling, redness, and plaque induration/infiltration (thickness) in each region, yielding an overall score of 0 for no psoriasis to 72 for the most severe disease (Fredriksson and Pettersson 1978). The PASI has been the most frequently used endpoint and measure of psoriasis severity in clinical trials (EMA 2004; Menter et al. 2008). A clinically meaningful response is a PASI 75, which represents at least a 75% decrease (improvement) from the baseline PASI score. Higher levels of clearance (PASI 90), as well as complete resolution of psoriasis (PASI 100), have become additional endpoints because of the increasing recognition of the association of higher clearance with greater health-related quality of life (HRQoL) (Puig 2015).

9.1.2. Secondary Efficacy Assessments

Secondary efficacy assessments will include the following:

9.1.2.1. Static Physician's Global Assessment

Both sPGA (0) and sPGA (0,1) will be assessed at various time points up to Week 52. For assessment description, see Section 9.1.1.1.

9.1.2.2. Psoriasis Area and Severity Index

PASI 75, PASI 90, and PASI 100 will be assessed at various time points up to Week 52. PASI 75, 90, and 100 are the percentage improvements in PASI (75%, 90%, and 100%, respectively). For assessment description, see Section 9.1.1.2.

9.1.2.3. Body Surface Area

Percent BSA will be evaluated as the percent involvement of psoriasis on each patient's BSA on a continuous scale from 0% (no involvement) to 100% (full involvement), where 1% corresponds to the size of the patient's hand (including the palm, fingers, and thumb) (National Psoriasis Foundation 2016).

9.1.2.4. Nail Psoriasis Severity Index

The Nail Psoriasis Severity Index (NAPSI) is used to evaluate the severity of fingernail bed psoriasis and fingernail matrix psoriasis by area of involvement in the fingernail unit. In this study, only fingernail involvement will be assessed. The fingernail is divided with imaginary horizontal and longitudinal lines into quadrants. Each fingernail is given a score for fingernail bed psoriasis (0 to 4) and fingernail matrix psoriasis (0 to 4) depending on the presence (score of 1) or absence (score of 0) of any of the features of fingernail bed and fingernail matrix psoriasis in each quadrant. The NAPSI score of a fingernail is the sum of scores in fingernail bed and fingernail matrix from each quadrant (maximum of 8). Each fingernail is evaluated, and the sum of all the fingernails is the total NAPSI score (range, 0 to 80).

9.1.2.5. Psoriasis Scalp Severity Index

The Psoriasis Scalp Severity Index (PSSI) measures the affected scalp area and the severity of clinical symptoms. The PSSI is a composite score derived from the sum of scores for erythema, induration, and desquamation multiplied by a score for the extent of scalp area involved (range, 0 to 72). Higher scores indicate worse severity (Thaçi et al. 2015).

9.1.2.6. Palmoplantar Psoriasis Severity Index

The Palmoplantar Psoriasis Severity Index (PPASI) is a composite score derived from the sum of scores for erythema, induration, and desquamation multiplied by a score for the extent of palm and sole area involvement (range, 0 to 72).

9.1.2.7. Health Outcomes Assessments

The following patient-reported questionnaires will be administered according to the Schedule of Activities (Section 2) in countries where the questionnaires have been translated into the native language of the region and linguistically validated. These assessments should be completed before administration of investigational product; before the patient's clinical examination; before the patient receives any tests or results; and before the patient's health, health data, or emotions are discussed.

9.1.2.7.1. Dermatology Life Quality Index

The Dermatology Life Quality Index (DLQI) is a validated, dermatology-specific, patient-reported measure that evaluates a patient's HRQoL. This questionnaire has 10 items that are grouped into 6 domains, namely symptoms and feelings, daily activities, leisure, work and school, personal relationships, and treatment. The recall period of this scale is over the "last

week” Response categories include “not at all,” “a little,” “a lot,” and “very much,” with corresponding scores of 0, 1, 2, and 3, respectively, and unanswered (“not relevant”) responses scored as “0.” The total score ranges from 0 to 30 (less to more impairment) (Finlay and Khan 1994; Basra et al. 2008). A DLQI total score of 0 to 1 is considered as having no effect on a patient’s HRQoL, and a 5-point change from baseline is considered as the minimal clinically important difference (MCID) threshold (Khilji et al. 2002; Hongbo et al. 2005).

9.1.2.7.2. European Quality of Life–5 Dimensions–5 Levels–Psoriasis

The European Quality of Life–5 dimensions–5 levels (EQ–5D–5L) questionnaire is a widely used, generic questionnaire that assesses health status (EuroQol Group 1990; Herdman et al. 2011). The questionnaire consists of 2 parts. The first part assesses 5 dimensions (mobility, self-care, usual activities, pain/discomfort and anxiety/depression) that have 5 possible levels of response (no problems, slight problems, moderate problems, severe problems, extreme problems). This part of the EQ–5D–5L can be used to generate a health state index. The health state index score is calculated based on the responses to the 5 dimensions, providing a single value on a scale from less than 0 (where zero is a health state equivalent to death; negative values are valued as worse than dead) to 1 (perfect health), with higher scores indicating better health utility. The second part of the questionnaire consists of a visual analog scale on which the patient rates their perceived health state from 0 (the worst health you can imagine) to 100 (the best health you can imagine). The study will use the EQ–5D–5L–Psoriasis (EQ–5D–5L–PSO), which is a version of the EQ–5D–5L with two additional items related to psoriasis: skin irritation and self-confidence (Swinburn et al. 2013).

9.1.2.7.3. Work Productivity and Activity Impairment Questionnaire: Psoriasis

The Work Productivity and Activity Impairment-Psoriasis (WPAI-PSO) Questionnaire is a patient-reported instrument developed to measure the impact on work productivity and regular activities attributable to a specific health problem (psoriasis). It contains 6 items that measure: 1) employment status, 2) hours missed from work due to the psoriasis, 3) hours missed from work for other reasons, 4) hours actually worked, 5) degree of health affected-productivity while working, and 6) degree of health affected-productivity in regular unpaid activities. Four scores are calculated from the responses to these 6 items: absenteeism, presenteeism, work productivity loss, and activity impairment. Scores are calculated as impairment percentages (Reilly et al. 1993), with higher numbers indicating greater impairment and less productivity, that is, worse outcomes.

9.1.2.7.4. Psoriasis Symptoms Scale

The Psoriasis Symptoms Scale (PSS) is a patient-administered assessment of 4 symptoms (itch, pain, stinging, and burning); 3 signs (redness, scaling, and cracking); and 1 item on discomfort related to symptoms/signs. Respondents are asked to answer the questions based on their psoriasis symptoms.

The overall severity for each individual symptom/sign from the patient’s psoriasis is indicated by selecting the number from a numeric rating scale (NRS) of 0 to 10 that best describes the worst level of each symptom/sign in the past 24 hours, where 0=no symptom/sign and 10=worst imaginable symptom/sign.

The symptom severity scores, ranging from 0 to 10, are the values of the selected numbers indicated by the patient on the instrument's horizontal scale. Each of the 8 individual items will receive a score of 0 to 10 and will be reported as item scores for itch, pain, stinging, burning, redness, scaling, cracking, and discomfort. In addition, a symptoms score ranging from 0 (no symptoms) to 40 (worst imaginable symptoms), and a signs score of 0 (no signs) to 30 (worst imaginable signs) will be reported.

